10. SAFETY MONITORING

Safety will be monitored by physical examinations, vital signs, clinical laboratory tests (i.e., chemistries, hematology, coagulation studies, and urinalysis), CT and MRI, ECGs, and adverse event (AE) assessment. Safety assessments will compare the groups on the basis of all AEs, changes in laboratory and vital signs values, and results of physical examinations. AE data will be listed individually, and will be descriptively summarized by body system, preferred terms within a body system, and treatment dose.

10.1 Adverse Events

For the purposes of this study, an adverse event (AE) is any untoward occurrence associated with the use of a drug in humans whether or not considered drug related. FDA, Office of Human Research Protection (OHRP), and NeuroNEXT CIRB requirements for reporting AEs will be followed. Adverse events are generally detected in two ways:

- Clinical – Symptoms reported by the subject or signs determined on examination
- Ancillary Tests – Abnormalities of vital signs, laboratory tests, and other diagnostic procedures (other than the outcome measures: the results of which are not being captured as AEs).

If discernible at the time of completing the AE source documentation, a specific disease or syndrome rather than individual associated signs and symptoms should be identified by the Site Investigator and recorded in the AE documentation. However, if an observed or reported sign, symptom, or clinically significant laboratory anomaly is not considered by the Site Investigator to be a component of a specific disease or syndrome, then it should be recorded as a separate AE in the source documentation. Clinically significant laboratory abnormalities, such as those that require intervention, are those that are identified as such by the Site Investigator.

Each clinical study site's Principal Investigator and research team (co-investigators, research nurse, clinical trial coordinator) are responsible for identifying and reporting AEs through the NeuroNEXT Online Adverse Event Reporting System. The AE definitions and reporting procedures used for this study comply with all applicable United States Food and Drug Administration (FDA) regulations and International Conference on Harmonization (ICH) guidelines. The Site Investigator will carefully monitor each subject throughout the study for possible AEs. All AEs will be documented on CRFs designed specifically for this purpose. It is important to report all AEs, especially those that result in permanent discontinuation of the investigational product being studied, whether serious or non-serious. Local site investigators are also required to fulfill all reporting requirements of their local institutions.

Subjects who sign consent and receive investigational treatment will be monitored for AEs from the time they sign consent through Day 7. Any AEs that occur prior to informed consent should be included in the subject's medical history. This study will utilize the CTCAE version 4.03 coding system for adverse event recording. AEs reported using CTCAE will be recoded into MedDRA terms by the DCC, with the exception that events of "Intracranial Hemorrhage", "Cerebral Hematoma", or "SICH" are coded as "Cerebral Hemorrhage" and events of "Infarct Extending" are coded as "Cerebrovascular Accident" (per request of PPI).

At each visit (including telephone interviews), the subject will be asked "Have you had any problems or symptoms since your last visit?" in order to determine the occurrence of AEs. If the subject reports an AE, the Investigator will determine:

- Type of event
- Date on onset and resolution (duration)
- Severity (mild, moderate, severe, life-threatening, results in death)
- Seriousness (does the AE meet the definition of an SAE)
- Causality, relation to investigational product and disease
- Action taken regarding investigational product
- Outcome

All clinical AEs are recorded in the AE data entry template in the subject's study binder. The site should fill out the AE data entry template and enter the information into the Online Adverse Event Reporting System (AERS) within 5 working days / 7 calendar days of the site learning of a new AE or receiving an update on an existing AE. Entries in the AE data entry template will include the following:

- Name and severity of the AE
- Date of onset
- Date of resolution
- Relationship to study drug
- Action taken

- Primary outcome of event

The severity of all AEs will be graded according to CTCAE, version 4.03. Any AE not listed in the CTCAE will be graded as follows:

- Grade 1 – Mild: Transient or mild discomfort; No limitation in activity; No medical intervention/therapy required
- Grade 2 – Moderate: Mild to moderate limitation in activity; Some assistance may be needed; No or minimal medical intervention/therapy required
- Grade 3 – Severe: Marked limitation in activity, some assistance usually required; Medical intervention/therapy required; Hospitalizations possible
- Grade 4 – Potentially Life-Threatening: Extreme limitation in activity; Significant assistance required; Significant medical intervention/therapy required; Hospitalization or hospice care probable
- Grade 5 – Death: The AE results in death

The relationship of the AE to the investigational product should be specified by the Site Investigator, using the following definitions:

- Definitely Related: The reaction follows a reasonable temporal sequence from administration of investigational product; Follows a known or expected response pattern to the investigational product; and is confirmed by improvement on stopping or reducing the dosage of the investigational product, and reappearance of the reaction on repeated exposure. (suspected ADR)
- Probably Related: The reaction follows a reasonably temporal sequence from administration of investigational product; Is confirmed by discontinuation of the investigational product or by re-challenge; and cannot be reasonably explained by the known characteristics of the subject's clinical state. (suspected ADR)
- Possibly Related: The reaction follows a reasonably temporal sequence from administration of the investigational product and follows a known response pattern to the suspected investigational product; Reaction could have been produced by the investigational product or could have been produced by the subject's clinical state or by other modes of therapy administered to the subject. (suspected ADR)
- Unlikely to be Related: The reaction has little or no temporal sequence from administration of the investigational product, and/or a more likely alternative etiology exists.
- Unrelated: Concomitant illness, accident, or event with no reasonable association with treatment.

For the purposes of this study, an AE is considered to be treatment-related if the attribution is possible, probable, or definite. All AEs should be followed until resolution or a new baseline is established, but no longer than study Day 90.

Headache has been identified as an AE that we would like to further characterize. Therefore, all headaches that start after signing of the ICF should be documented as AEs, and Investigators should also complete the Headache Record CRF. A new AE form, and new Headache Record should be completed for each new headache during the first seven days. Headaches that start prior to signing of the ICF, and do not worsen, should be reported only on the Medical History CRF and the Headache Record CRF should not be completed. If, however, a headache begins prior to consent and later worsens it should be reported as an AE and the Headache Record CRF should be completed.

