Four dose levels will be considered for this study: 120, 240, 360, and 540 µg/kg. Following completion of tPA infusion, or initiation of mechanical thrombectomy (arterial puncture), whichever is sooner, eligible adult subjects will receive 3K3A-APC or placebo 30 to 120 minutes later given as a 15 minute infusion. Subjects will receive another 15 minute infusion of study treatment every 12 hours (+/- 1 hour) for up to 5 total doses (or until discharge, whichever occurs first). It is preferable not to skip doses of study drug, and should a dose need to occur outside of the +/- 1 hour window (which will be reported as a protocol deviation), doses should never be given within 8 hours of one another.

For the purposes of this study, we assume an established background symptomatic intracerebral hemorrhage (SICH) rate of 3-6% (Wahlgreen et al, 2007; Hacke et al, 2008; Berkhemer et al, 2015; Campbell et al, 2015; Goyal et al, 2015; Saver et al, 2015). Correspondingly, this study aims to identify the highest dose with a DLT rate of 10% or less. Subjects will be enrolled to 3K3A-APC dose cohorts in groups of four (three to specified treatment dose and one to placebo). Subjects will generally be enrolled at the dose estimated from the model at that time, based on the assumed original dose-response model and all prior observed data to date, as the highest dose with a DLT rate of 10% or less. However, the initial cohort will start at the lowest dose (120 µg/kg) and the dose level may be escalated by no more than one dose between consecutive cohorts (there are no restrictions on dose level de-escalation). Intra-subject dose modification is not permitted during the study. After the final group of subjects is enrolled, the final MTD will be defined as the highest dose with an estimated toxicity probability less than or equal to the target toxicity level of 10%.

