2. PRIMARY ENDPOINT

The primary objective of the study is to evaluate the safety of multiple ascending intravenous (IV) doses of 3K3A-APC following tPA administration in subjects who have experienced moderate to severe acute hemispheric ischemic stroke. Safety will be assessed by defining dose limiting toxicities (DLTs), which will be graded using the National Cancer Institute (NCI) Common Terminology Criteria for Adverse Events (CTCAE), Version 4.03.

DLTs will be assessed from the first dose to 48 hours following the last dose of study treatment (unless specified below), and defined as any of the following AEs that have an attribution of “related” to study treatment (possibly, probably and definitely):

- An activated partial thromboplastin time (aPTT) that reaches 2x the upper limit of normal (ULN) at 1 hour post-dose. The ULN range is defined locally by the site laboratory.
- Symptomatic intracranial hemorrhage (SICH) defined as blood present on CT or MRI brain image that is associated with clinical worsening that meets the definition of neuroworsening (4 or more point increase on the NIHSS; see section 10.3 for definition) *and* in the opinion of the investigator represents a clinically significant change that can be attributed to the hemorrhage. Subarachnoid hemorrhage that occurs in subjects who receive mechanical thrombectomy will NOT be considered a DLT, and instead will be evaluated in an exploratory analysis upon study completion.
- Findings that meet all of the following three components (Hy’s Law):
 - $\geq 3x$ ULN of alanine aminotransferase (ALT) or aspartate aminotransferase (AST)
 - Serum total bilirubin (TBL) $> 2x$ ULN, without initial findings of cholestasis [serum alkaline phosphatase (ALP) activity $> 2x$ ULN]
 - And, no other reason can be found to explain the combination of increased aminotransferase (AT) enzymes and TBL, such as viral hepatitis A, B, or C, pre-existing or acute liver disease, or another drug capable of causing the observed injury.
- Any other bleeding event classified as serious by the Investigator, or any bleeding that required the administration of more than 2 units of packed red cells over any two consecutive days.
- Any Grade 3 laboratory value that, in the opinion of the investigator, is related to study treatment.

- Any adverse event that, in the opinion of the investigator, is related to study treatment and leads to cessation of further dosing.

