10.3 Neuroworsening

For the purposes of this protocol, the incidence of “neuroworsening” is expected to be significant in this trial of acutely ill stroke patients. Per the protocol, neurological worsening is defined as a 4 or more point increase on the NIHSS, as compared to the most recent NIHSS, that lasts for more than 8 hours, is confirmed by a repeat NIHSS, follows administration of study drug, is resulting from edema, hemorrhage, hydrocephalus, and/or extending infarct, and is not felt to be attributable to non-neurological causes, such as iatrogenic sedation or medical co-morbidities. The cause of the neuroworsening will be captured as a serious adverse event, and must be declared by the site PI as hemorrhage, progressive cerebral edema, new infarct, or hydrocephalus. If occurring during the DLT reporting period, will be evaluated by the IMM as a potential DLT. For each case, sufficient imaging will be selected by the CSS Investigator, de-identified, and submitted to the IMM for review so that he can confirm the reason for neuroworsening. Refer to the ‘Imaging Plan’ for details. The Site Investigator will be asked to give primary and contributing causes of the worsening, and to gauge the depth of worsening by performing a NIHSS as close to the nadir as possible. The IMM will review all cases of neuroworsening, and will refer suspected cases of SICH to the SRC for adjudication. Refer to the ‘Safety Management Plan’ for further details.

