10.8 Safety Analyses

In addition to the determination of an MTD, additional safety assessments will involve a comparison of treatment-related AEs and SAEs across all 3K3A-APC treated subjects (regardless of dose) versus placebo. First, the percentage of subjects who experience any treatment-related AE or SAE in each group will be compared using a Fisher's exact test. If the null hypothesis is rejected, with a greater frequency observed in the 3K3A-APC group, we will conclude that 3K3A-APC was associated with a significantly greater frequency of treatment-related AEs. If the hypothesis is not rejected, we will conclude that the study does not provide sufficient evidence to conclude that 3K3A-APC was associated with a significantly greater frequency of treatment-related AEs. In addition to an overall comparison, this hypothesis will be repeated for the percentage of subjects having at least one treatment-related AE within each MedDRA system organ class (SOC). If there are significant differences between groups within any specific SOC, then additional tests will compare differences across groups for specific MedDRA preferred terms in order to further explore the cause of observed differences.

In addition to the comparison of percentages in the manner described above, the rates of treatment-related AEs in each group will be compared using the following Poisson regression model:

$$\log\left(\frac{Y_i}{T_i}\right) = \beta_0 + \beta_1 x_{1i} + \epsilon_i$$

where

- Y_i represents the number of treatment related SAEs experienced by the i^{th} subject.
- T_i represents the number of days between the date of randomization and the date of last follow-up for the i^{th} subject.
- $x_i = 1$ if i^{th} subject was randomized to one of the 3K3A-APC dose groups, and 0 if the subject was randomized to placebo group
- ϵ_i is random error for the i^{th} subject

To determine if the rate of treatment related SAEs differ across treatment group we will test the following hypothesis:

$$H_0: \beta_1 = 0 \text{ vs. } H_A: \beta_1 \neq 0$$

If the null hypothesis is rejected, the direction of β_1 will indicate the direction of the observed effect. Values of $\beta_1 > 0$ indicate an increased rate of treatment-related AEs associated with the 3K3A-APC group, while values of $\beta_1 < 0$ indicate a decreased rate of treatment-related AEs associated with the 3K3A-APC group.

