Treatment-related SAEs will be analyzed in the same manner described above. Additional safety analyses will assess all treatment-emergent AEs, treatment-emergent SAEs, unanticipated SAEs, treatment-related & unanticipated SAEs, neuroworsening events, DLTs, and deaths in a similar manner. Finally, all safety analyses will be repeated for each pairwise comparison of subjects in each specific 3K3A-APC dose groups versus the placebo group.

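### SICH, whose assumed background rate motivates the 10% DLT ceiling, has no between-arm comparison of its own

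*SAP*

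**What the plan says.** SAP 1 ties the DLT target to the bleeding expected without the drug: "we assume an established background symptomatic intracerebral hemorrhage (SICH) rate of 3-6" (percent). On that basis the trial seeks the highest dose with a DLT rate of at most 10%. Three other parts of the SAP decide how SICH is then analysed.

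- **Coding (SAP 10.1).** Events are recoded from CTCAE to MedDRA with two exceptions. One is that "events of 'Intracranial Hemorrhage', 'Cerebral Hematoma', or 'SICH' are coded as 'Cerebral Hemorrhage".
- **Comparisons (SAP 10.8).** With Fisher's exact test, "the percentage of subjects who experience any treatment-related AE or SAE in each group will be compared". The comparison is repeated within each system organ class (SOC). Terms come last: "If there are significant differences between groups within any specific SOC, then additional tests will compare differences across groups for specific MedDRA preferred terms". The scheme is extended to treatment-emergent events and to a list ending in "neuroworsening events, DLTs, and deaths in a similar manner". SICH is not on that list. On dose levels, the section adds that "all safety analyses will be repeated for each pairwise comparison of subjects in each specific 3K3A-APC dose groups versus the placebo group".
- **Definition and review (SAP 2, 10.3, 10.4).** SICH is blood on CT or MRI together with "clinical worsening that meets the definition of neuroworsening", in the investigator's opinion a clinically significant change due to the hemorrhage. The medical monitor reviews every neuroworsening case and "will refer suspected cases of SICH to the SRC for adjudication". SICH counts as a DLT when judged related to study treatment.

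**The concern.** The drug is a protein C variant given soon after tPA or thrombectomy, so a reader of the final report will want to know how many subjects had SICH on drug and on placebo. The plan does not produce that contrast.

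- The recode removes the distinction between symptomatic and other intracranial bleeds before any term is tabulated or tested.
- The merged term is tested only if its SOC differs, so the test depends on unrelated events in the same class.
- Neuroworsening pools hemorrhage with edema, infarct extension and hydrocephalus.
- DLTs need a relatedness judgement, which is hard to make for a bleed after tPA or thrombectomy. They also include aPTT and other laboratory events.
- Both composites close early. DLTs are assessed to 48 hours after the last dose (SAP 2), and Protocol 9.4.1.3 says that later deterioration is not neuroworsening. SAEs are collected to Day 30 (SAP 10.2). A non-fatal symptomatic bleed in between is in neither composite. It enters comparisons only through all-event and SOC totals or the merged term.

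**Working it through.** **Inputs from the documents.** The 22 cohorts give 22 × 3 = 66 treated and 22 × 1 = 22 placebo subjects. The approximate total of 115 gives 115 − 66 = 49 placebo subjects if all extra subjects receive placebo. Headache in Phase 1 ran at 54% on drug and 7% on placebo (Protocol 2.5).

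**Assumptions.** SICH is 5% on placebo (inside 3-6%) and 10-25% on drug. The rates of other events are as shown below. Tests are two-sided at 0.05, because SAP 6 gives that level for key secondary objectives and none for safety.

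**1. The plan's own between-arm power.** SAP Table 6 concerns Day 30 MRI bleeding, not SICH. It is the only between-arm power in the documents. Power = Φ[(|p1 − p2| − 1.96·s0)/s1], where s0 is the pooled and s1 the unpooled standard error. For 10% vs 30% with 66/22:

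- pooled rate = (6.6 + 6.6)/88 = 0.15
- s0 = √(0.15 × 0.85 × (1/66 + 1/22)) = 0.0879
- s1 = √(0.09/66 + 0.21/22) = 0.1044
- power = Φ[(0.20 − 0.1723)/0.1044] = Φ(0.265) = 60.5%, against 61% stated

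All 18 cells agree within one point. No such figure is given for SICH.

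**2. SICH compared directly** (exact enumeration of Fisher's test, placebo 5%):

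| SICH on drug | 66 vs 49 | 66 vs 22 |
|---|---|---|
| 10% | 12% | 1% |
| 15% | 36% | 10% |
| 20% | 63% | 29% |
| 25% | 84% | 51% |

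**3. SICH inside neuroworsening** (66 vs 49, SICH 20% vs 5%, other causes at rate o in both arms). If other causes are independent of SICH, the composite rate is 1 − (1 − o)(1 − p). If they are exclusive, it is o + p.

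| o | Independent: rates, power | Exclusive: rates, power |
|---|---|---|
| 10% | 28% vs 14.5%, 37% | 30% vs 15%, 44% |
| 20% | 36% vs 24%, 25% | 40% vs 25%, 35% |

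For SICH of 15% vs 5%, the independent case gives 19% and 13%, against 36% directly.

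**4. The SOC test that must be significant first** (66 vs 49, SICH 20% vs 5%, independent other events).

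- Other events equal at 30%: 1 − 0.7 × 0.8 = 44% vs 1 − 0.7 × 0.95 = 33.5%, significant in 17% of trials.
- Other events equal at 80%: 84% vs 81%, significant in 5%.
- Other events at 54% vs 7%, as headache in Phase 1: 63.2% vs 11.65%, significant in over 99%.
- Other events at 54% vs 30%: significant in 87%. At 54% vs 40%: 53%.

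The result runs from 5% to over 99% on inputs that the documents do not supply, so no single figure can be given for this step.

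**The case against.** A reader might infer that an excess of SICH on drug would usually go untested, or that the SOC condition would hide most true signals. The documents do not support this.

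- Every SICH meets the neuroworsening definition, and a related SICH is a listed DLT. SAP 10.8 compares both, pooled and by dose, without an SOC condition. The neuroworsening comparison also needs no relatedness judgement. SICH is diluted, not left out.
- Low SOC-level power follows only if other events in the class are equal between arms. The documents do not give SOC membership or background rates. If headache shares the class and keeps even part of its Phase 1 excess, the merged term may well be tested. Moreover, the SOC condition is first written for treatment-related events, so an all-cause background applies only to the treatment-emergent repeat.
- The documents give no rate for asymptomatic bleeds reported as AEs. SAP 10.1 does not capture outcome-measure results as AEs, so the dilution within the merged term cannot be sized.
- AEs are listed individually and summarized by preferred term and dose in any case (SAP 10). The underlying SICH records survive the recode.
- The primary analysis estimates a maximum tolerated dose without formal testing (SAP 6), and a direct SICH test would itself miss most moderate excesses.

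All of this stands against the stronger reading. It does not close the gap. The summary table shows only the merged term, the composites do not isolate SICH, and bleeds after the DLT window fall outside both. If a headache excess does lead to a test, the merged term is tested, not SICH.

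**Conclusion.** The point holds as a reporting and analysis gap: the plan defines, reviews and adjudicates SICH but never contrasts it between arms. In the illustrative case of 20% vs 5% with 66 and 49 subjects, reliance on neuroworsening lowers power from 63% to about 25-44%. This rests on assumed SICH rates, other causes of neuroworsening at 10-20% in both arms, two-sided 0.05, and all extra subjects being on placebo. With 22 placebo subjects, direct power is 29%. How often the SOC condition would block the merged term cannot be fixed from the documents. Because power is low for moderate excesses, the main loss is the missing estimate and its interval rather than a missing p-value.

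**What to change.** 1. In SAP 10.1, keep SICH (SAP 10.4 definition, as reviewed by the medical monitor and Safety Review Committee) as a separate flag set outside the MedDRA recode. The recode itself can stay.
2. In SAP 10.8, add a row for SICH of any attribution, treated vs placebo and each dose vs placebo, outside the SOC condition. Give counts, risk difference and exact confidence interval as the main output, with Fisher's p-value as supportive. State how subarachnoid hemorrhage after thrombectomy is counted: SAP 2 excludes it from DLTs, but SAP 10.4 is silent.
3. Add a second row for symptomatic intracranial hemorrhage reported as an SAE after the DLT window through Day 30, which the neuroworsening-based definition leaves out.

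The cost is SAP wording and one short table. Sites already declare the cause of neuroworsening, the medical monitor checks it on images and reviews all SAEs, and the committee adjudicates suspected SICH. The downside is one or two more unadjusted safety comparisons, with low power for moderate excesses (12% for 10% vs 5% with 66 and 49 subjects). A non-significant result must therefore not be read as evidence of no excess.
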